7.3.1 Primary endpoint analyses

Primary analyses

The statistical model used for the analysis of the primary endpoints will be an analysis of variance (ANOVA) model on the logarithmic scale. That is, the PK endpoints will be log-transformed (natural logarithm) prior to fitting the ANOVA model. This model will include effects accounting for the following sources of variation: 'subjects' and 'formulation'. The

Proprietary confidential information © 2018 Boehringer Ingelheim International GmbH or one or more of its affiliated companies

effect 'subjects' will be considered as random, whereas 'formulation' will be considered as fixed. The model is described by the following equation:

$y_{km} = \mu + s_m + \tau_k + e_{km}$, where

y_{km} = logarithm of response (dose normalized primary endpoint, see Section [2.1.2](#))
measured on subject m receiving formulation k,

μ = the overall mean,

s_m = the effect associated with the mth subject,
 $m = 1, 2, \dots, n$

τ_k = the kth formulation effect (either tablet or i.v.), $k = 1, 2$,

e_{km} = the random error associated with the mth subject who received
formulation k.

Point estimates for the ratio of the geometric means (test/reference) for the primary endpoints (see Section [2.1](#)) and their two-sided 90% confidence intervals (CIs) will be provided.

For each endpoint, the difference between the expected means for log(T)-log(R) will be estimated by the difference in the corresponding adjusted means (Least Squares Means). Additionally their two-sided 90% confidence intervals will be calculated based on the residual error from the ANOVA and quantiles from the t-distribution. These quantities will then be back-transformed to the original scale to provide the point estimate and 90% CIs for each endpoint.

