Clinical Trial Protocol

Document Number:		c22193484-01
EudraCT No.	2018-003103-19	
BI Trial No.	1407-0033	
BI Investigational Medicinal Product	BI 730357	
Title	Investigation of pharmacokinetics and absolute oral bioavailability of BI 730357 administered as an oral dose with an intravenous microtracer dose of BI 730357 BS (C-14) in healthy male volunteers	
Lay Title	A study in healthy men to measure the amount of BI 730357 in the blood when taken as a tablet	
Clinical Phase	I	
Clinical Trial Leader	
Phone: Fax:
	
Principal Investigator	
Phone: Fax:
	
Status	Final Protocol	
Version and Date	Version: 1.0	Date: 29 Nov 2018
Page 1 of 64		

Proprietary confidential information © 2018 Boehringer Ingelheim International GmbH or one or more of its affiliated companies. All rights reserved. This document may not - in full or in part - be passed on, reproduced, published or otherwise used without prior written permission
		

Proprietary confidential information © 2018 Boehringer Ingelheim International GmbH or one or more of its affiliated companies

CLINICAL TRIAL PROTOCOL SYNOPSIS

Company name	Boehringer Ingelheim
Protocol date	29 Nov 2018
Revision date	Not applicable
BI trial number	1407-0033
Title of trial	Investigation of pharmacokinetics and absolute oral bioavailability of BI 730357 administered as an oral dose with an intravenous microtracer dose of BI 730357 BS (C-14) in healthy male volunteers
Principal Investigator:	
Trial site	
Clinical phase	I
Trial rationale	This trial is intended to examine the absolute oral bioavailability of BI 730357 as tablet formulation for oral administration. The data are considered necessary to further understand the pharmacokinetics of BI 730357.
Trial objective	To determine the absolute oral bioavailability of BI 730357 after administration of 50 mg BI 730357 as tablet and 100 µg BI 730357 BS (C-14) as intravenous microtracer
Trial design	Non-randomized, open-label, single period, single arm design
Trial endpoints:	Primary endpoints: AUC _{0-∞} [C-14]BI 730357 BS (after i.v. administration) AUC _{0-∞} BI 730357 (after p.o. administration) Secondary endpoints: None defined.

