2. TRIAL OBJECTIVES AND ENDPOINTS

2.1 MAIN OBJECTIVES, PRIMARY AND SECONDARY ENDPOINTS

2.1.1 Main objectives

The main objective of this trial is to investigate the absolute oral bioavailability of 50 mg BI 730357 administered as tablet (test treatment, T) compared with 2 µg of [C-14]BI 730357 BS administered as intravenous microtracer. The total dose administered i.v. is a mixture of 2 µg labelled [C-14]BI 730357 BS mixed with 98 µg of unlabelled BI 730357 (reference treatment, R).

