3. DESCRIPTION OF DESIGN AND TRIAL POPULATION

3.1 OVERALL TRIAL DESIGN AND PLAN

This Phase 1 study will be performed as a non-randomised, open-label, single period, single arm trial in healthy male subjects in order to compare the test treatment (T) to the reference treatment (R). Treatment T will be one oral tablet of 50 mg BI 730357 (intended clinical formulation (iCF)). Treatment R will be an intravenous microtracer infusion of 100 µg BI 730357 BS (C-14) consisting of 2 µg labelled [C-14]BI 730357 BS mixed with 98 µg unlabelled BI 730357 in 10 mL i.v. solution (10 µg BI 730357 BS (C-14) /mL). Both treatments will be given in the fasted state. For details, refer to Section [4.1](#).

Drug administration in treatment R will start 1.25 hours after drug administration in treatment T, i.e. at the time of the expected t_{max} of treatment T.

An overview of all relevant trial activities is provided in the [Flow Chart](#). For visit schedule and details of trial procedures at selected visits, refer to Sections [6.1](#) and [6.2](#), respectively.

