4.1.4 Drug assignment and administration of doses for each subject

This trial is a non-randomised, open-label, single period, single arm trial. All subjects will receive the same treatments. The treatments to be evaluated are outlined in Table [4.1.4: 1](#) below.

Table 4.1.4: 1 Dosage and treatment schedule

Treatment	Substance	Formulation	Unit strength	Dosage	Total dose
T (Test)	BI 730357	Film-coated tablet	50 mg	1 tablet as single dose on Day 1	50 mg
R (Reference)	BI 730357 BS (C-14)	i.v. solution	10 µg/mL	i.v. infusion of 10 mL over 15 min on Day 1	100 µg

Administration of treatment T will be performed after subjects have fasted overnight; fasting is to start no later than 10 h before the scheduled dosing.

The oral medication (treatment T) will be administered as a single oral dose together with about 240 mL of water to a subject in the sitting/standing position under supervision of the investigating physician or an authorised designee.

From administration of treatment T until 5 hours thereafter, subjects are not allowed to lie down (i.e. no declination of the upper body of more than 45 degrees from upright posture) except when needed for study assessments or when indicated by the investigator. During the intravenous infusion subjects will be in a semi supine position.

Proprietary confidential information © 2018 Boehringer Ingelheim International GmbH or one or more of its affiliated companies

The microtracer (treatment R) will be administered starting 1.25 h after treatment T as a constant intravenous infusion over 15 min to a subject in semi supine position under supervision of the investigating physician or an authorised designee. Start and end time of the infusion will be recorded. For administration of the intravenous microtracer solution an indwelling catheter is placed into an arm vein of the subject and will be kept patent with a saline infusion. A second indwelling catheter used for collection of blood samples will be placed on the contralateral arm. The handling instructions for the intravenous microtracer will be filed in the ISF.

For drug administrations, the so-called four-eye principle (two-person rule) should be applied. For this, one authorised employee of the trial site should witness the administration of trial medication, and – if applicable – its preparation (e.g. reconstitution), if correct dosage cannot be ensured otherwise.

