7.2 NULL AND ALTERNATIVE HYPOTHESES

The absolute bioavailability of 50 mg orally administered BI 730357 compared with 2 µg of labelled [C-14]BI 730357 administered as intravenous microtracer (mixed with 98 µg unlabelled BI 730357) will be estimated by the ratio of the geometric means (test/reference) for the dose-normalized primary PK endpoints. Additionally, their 2-sided 90% confidence intervals (CIs) will be provided. This method corresponds to the two one-sided t-test procedure, each at the 5% significance level. Since the main focus is on estimation and not testing, a formal hypothesis test and associated acceptance range is not specified.

Confidence intervals have to be interpreted in the perspective of the exploratory character of the study, i.e. confidence intervals are considered as interval estimates for effects.

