7.4 PRIMARY ENDPOINT

The analysis of secondary endpoints will be based on the PKS.

Analysis of absolute oral bioavailability of dose normalised primary endpoints will be performed as defined in Section 7.1 and 7.3.1 of the CTP.

The statistical model for the primary analysis defined in the CTP is an analysis of variance (ANOVA) model on the logarithmic scale.

Primary PK endpoints will also be assessed descriptively. The analysis of standard PK parameters is performed according to BI standards ([4](#)) [001-MCS-36-472_RD-01].

Exclusion of PK parameters

The ADS ADPP contains column variables APEXC and APEXCO indicating inclusion/exclusion (APEXC) of a PK parameter and an analysis flag comment (APEXCO). All analyses based on the PKS are based on PK parameter values which are not flagged for exclusion, i.e. with APEXC equal to "Included".

Exclusion of plasma concentrations

The ADS ADPC (PK concentrations per time-point or per time-interval) contains column variables ACEXC or ACEXCO indicating inclusion/exclusion (ACEXC) of a concentration

and an analysis flag comment (ACEXCO). Exclusion of a concentration depends on the analysis flag comment ACEXCO. For example, if ACEXCO is set to "ALL CALC", the value will be excluded for all types of analyses based on concentrations. If ACEXCO is set to "DESC STATS" the value will be excluded from descriptive evaluations per planned time point/time interval. If ACEXCO contains the addition "TIME VIOLATION" or "TIME DEVIATION", the value can be used for further analyses based on actual times. If ACEXCO is set to "HALF LIFE", the value will be excluded from half-life calculation only; the value is included for all other analyses. Excluded concentration itself will be listed in the CTR associated with an appropriate flag.

Further details are given in "Noncompartmental Pharmacokinetic / Pharmacodynamic Analyses of Clinical Studies" (4) and "Description of Analytical Transfer Files and PK/PD Data Files" (6).

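### Is the intravenous dose used to normalise the primary endpoint (2 µg or 100 µg, nominal or actual) left so open that the estimate of F could be wrong?

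*Protocol*

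**What the plan says.** Protocol 7.2 states that absolute bioavailability "will be estimated by the ratio of the geometric means (test/reference) for the dose-normalized primary PK endpoints". Protocol 7.3.1 gives the model response as the "logarithm of response (dose normalized primary endpoint", and points to 2.1.2, which names the AUC but no dose. The SAP adds no rule of its own: "Analysis of absolute oral bioavailability of dose normalised primary endpoints will be performed as defined in Section 7.1 and 7.3.1 of the CTP".

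The oral dose is given consistently: "Treatment T will be one oral tablet of 50 mg BI 730357". The reference dose is described in two ways:

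- Protocol 2.1.1 sets the tablet against the labelled part, "compared with 2 µg of [C-14]BI 730357 BS administered as intravenous microtracer". Protocol 7.1 and 7.2 do the same and add that it is mixed with 98 µg of unlabelled drug.
- The synopsis objective gives 100 µg of "BI 730357 BS (C-14) as intravenous microtracer". Protocol Table 4.1.4: 1 and the short label in SAP Table 6.1: 2 also use the 100 µg total.

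On the infusion itself, Protocol 4.1.4 says "Start and end time of the infusion will be recorded". It also applies a two-person rule to dosing and refers to handling instructions in the investigator site file. Protocol 4.1.8 requires records of quantities, batches and each subject's use, and of whether the planned doses were given. Protocol 7.3 lists a wrong dose among possible deviations relevant to pharmacokinetics. SAP 7.3 sends incomplete dosing to the report planning and database lock meeting.

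**The concern.** F is the trial's only primary result and there are no secondary endpoints. The intravenous dose enters F as a direct multiplier, so any error in it is a proportional error in F. Two figures that differ 50-fold appear under the name of the reference treatment, and the section that defines the model does not choose between them. Protocol 5.3.3.1 names the analyte measured by accelerator mass spectrometry (AMS) but not whether results are expressed as labelled mass or as total intravenous drug.

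A second worry is separate. Protocol 5.3.1 requires actual sampling times for the pharmacokinetic calculations, but no matching sentence requires the actual infused dose. If the nominal figure were used and part of the dose were lost in every subject, F would be too high, and nothing in the confidence interval would show it.

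**Working it through.** **1. Are 2 µg and 100 µg in conflict?** Inputs: the composition in the synopsis, Protocol 2.1.1, 3.1 and 4.1.1, and SAP Table 6.1: 2.

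- Labelled plus unlabelled: 2 + 98 = 100 µg.
- Volume times strength (Table 4.1.4: 1): 10 mL × 10 µg/mL = 100 µg.
- The ratio in Protocol 4.1.2: 50,000 µg / 100 µg = 500, as stated there.

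All the amounts agree. They describe one infusion.

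**2. Does the choice between them matter?** F = (AUC_po/D_po)/(AUC_iv/D_iv). Let A be the intravenous AUC in labelled mass.

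- Labelled mass over labelled dose: A/2.
- Total equivalents over total dose: (50 × A)/100 = A/2.

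A matched pair gives the same answer either way. Only a mismatch does harm, by a factor of 100/2 = 50. In an illustrative paired log-scale analysis of six subjects (assumed true F of 0.5), the matched estimate was 0.4866. Dividing the labelled AUC by 100 gave 0.4866 × 50 = 24.3, which is impossible for a bioavailability. The opposite mismatch would turn 0.5 into 0.5/50 = 0.01.

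**3. Which divisor do the documents point to?** The intravenous primary endpoint is the AUC of the labelled species (synopsis, 2.1.2). The AMS assay measures that species (5.3.3.1). Protocol 7.2 names the 2 µg labelled part as comparator in the same sentence that calls for dose normalisation. SAP 7.4 refers to Protocol 7.1, which names the same comparator.

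**4. What would a delivery shortfall do?** If a fraction s of the nominal dose is not delivered, AUC_iv falls by (1 − s) under linear kinetics, so F_est/F = 1/(1 − s). The documents give no loss figure, so s is assumed:

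| s | F_est/F |
|---|---|
| 1% | 1.010 |
| 2% | 1.020 |
| 5% | 1.053 |
| 10% | 1.111 |
| 15% | 1.176 |
| 20% | 1.250 |

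If only one of six subjects is short, the geometric mean ratio rises by (1/0.9)^(1/6) = 1.018 for 10% and by (1/0.7)^(1/6) = 1.061 for 30%. A shortfall common to all subjects moves the estimate and both limits by the same factor. In the illustration, 10% multiplied all three by 1.111 and left the residual error unchanged.

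**5. Scale against sampling error.** The 90% interval factor with n = 6 is exp(±t × sqrt(2 × ln(1 + CV²)/6)), with t(0.95, 5 df) = 2.015. The documents give no within-subject CV, so a range is assumed:

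| CV | 90% interval factor |
|---|---|
| 10% | 0.89 to 1.12 |
| 15% | 0.84 to 1.19 |
| 20% | 0.79 to 1.26 |
| 30% | 0.71 to 1.41 |

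A common 10% shortfall would be noticeable against the narrower of these intervals and modest against the wider ones.

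**The case for a change.** The best case for a change is that F rests entirely on this divisor, and the chain from SAP 7.4 to Protocol 7.3.1 to 2.1.2 ends without one. Dose records and deviation review can lead to exclusion or to a narrative, but no visible text says the divisor would be corrected. A small loss common to all subjects might never be flagged as anyone's deviation. The downward 50-fold mismatch would give a value between 0 and 1, so arithmetic alone would not expose it.

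Much of this is fair. The visible text does not state the divisor, the AMS reporting unit, or nominal versus actual dose. It does not follow that the delivered dose goes unmeasured or unused. The handling instructions and the sponsor's pharmacokinetic procedure are outside these documents. SAP 5.1, on the primary endpoint, is in the table of contents but its text is not in the public version. Those are the natural places for such a rule. The plan also contains no instruction to use the nominal dose.

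The obvious remedy does not reach its target either. Weighing the syringe before and after infusion counts drug left in the line as delivered and cannot detect adsorption to tubing. Losses of those kinds would still be there after the change.

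**Conclusion.** No change to the plan follows. The apparent dose contradiction is the labelled part and the total of one infusion, and the amounts reconcile exactly. The 50-fold figure arises only if the divisor and assay unit are mismatched. The endpoint, the assay and the statistical sections all point to the labelled 2 µg, and the bioanalytical results will carry their unit.

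What remains is an unwritten definition. An analyst calculating absolute bioavailability would match the dose to the assayed species and check the dosing records that Protocol 4.1.8 requires. If the nominal dose were used despite a real loss, the error would be 1/(1 − s): +5.3% at 5% and +11.1% at 10%, both assumed. That is a conditional risk with no loss figure behind it in the documents, in an exploratory estimation trial without an acceptance range. The conclusion assumes linear intravenous kinetics and that the text not available here does not prescribe a mismatched or uncorrected divisor.

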7.3.2 Secondary endpoint analysis

Not applicable.

7.3.4 Safety analyses

Safety will be analysed based on the assessments described in Section [2.2.2.2](#). All treated subjects (TS, refer to Section [7.3](#)) will be included in the safety analysis. Safety analyses will be descriptive in nature and based on BI standards. No hypothesis testing is planned.

For all analyses, the treatment actually administered (= treatment at onset) to the subject will be used (any deviations from the randomised treatment will be discussed in the minutes of the Report Planning Meeting).

Treatments will be compared in a descriptive way. Tabulations of frequencies/proportions will be used to evaluate categorical (qualitative) data, and tabulations of descriptive statistics will be used to analyse continuous (quantitative) data.

Measurements (such as ECG, vital signs, or laboratory parameters) or AEs will be assigned to treatments (see Section [4.1](#)) based on the actual treatment at the planned time of the measurement or on the recorded time of AE onset (concept of treatment emergent AEs). Therefore, measurements planned or AEs recorded prior to first intake of trial medication will be assigned to the screening period, those between first trial medication intake (test treatment) and beginning of reference treatment will be assigned to the test treatment period. Those between the start of infusion until the end of REP (see Section [1.2.3](#)) will be assigned to the combined test/reference treatment period. Events occurring after the REP but prior to next intake or end of trial termination date will be assigned to 'follow-up'. These assignments including the corresponding time intervals will be defined in detail in the TSAP. Note that AEs occurring after the last per protocol contact but entered before final database lock will be reported to Pharmacovigilance only and will not be captured in the trial database.

Additionally, further treatment intervals (analysing treatments) may be defined in the TSAP in order to provide summary statistics for time intervals, such as combined treatments, on-treatment totals, or periods without treatment effects (such as screening and follow-up intervals).

Adverse events will be coded using the Medical Dictionary for Regulatory Activities (MedDRA). Frequency, severity, and causal relationship of AEs will be tabulated by treatment, system organ class, and preferred term. SAEs, AESIs (see Section [5.2.6.1](#)), and other significant AEs (according to ICH E3) will be listed separately.

Previous and concomitant therapies will be presented per treatment group without consideration of time intervals and treatment periods.

Laboratory data will be compared to their reference ranges. Values outside the reference range as well as values defined as possibly clinically significant will be highlighted in the listings. Additionally, differences from baseline will be evaluated.

Vital signs or other safety-relevant data will be assessed with regard to possible on-treatment changes from baseline.

Relevant ECG findings will be reported as AEs.

7.4 INTERIM ANALYSES

No interim analysis is planned.

7.5 HANDLING OF MISSING DATA

7.5.1 Safety

It is not planned to impute missing values for safety parameters.

7.5.2 Pharmacokinetics

Handling of missing PK data will be performed according to the relevant Corporate Procedure ([001-MCS-36-472](#)).

PK parameters that cannot be reasonably calculated based on the available drug concentration-time data will not be imputed.

7.6 RANDOMISATION

Randomisation is not applicable in this open-label, single arm study. All subjects will receive the same treatment. Consecutive subject numbers will be assigned via the EDC system.

7.7 DETERMINATION OF SAMPLE SIZE

For this clinical trial, no prospective calculations of statistical precision or power have been made. The planned sample size of 6 subjects is judged as being adequate to get reliable results regarding the trial objectives. In case of observing dropouts, the sample size may increase to a maximum of 8 to have at least 6 subjects who completed the trial as per protocol.

For replacement rules, refer to Section [3.3.5](#).

8. INFORMED CONSENT, TRIAL RECORDS, DATA PROTECTION, PUBLICATION POLICY, AND ADMINISTRATIVE STRUCTURE

The trial will be carried out in compliance with the protocol, the ethical principles laid down in the Declaration of Helsinki, in accordance with the ICH Harmonized Guideline for Good Clinical Practice (GCP), relevant BI Standard Operating Procedures (SOPs), the EU directive 2001/20/EC and other relevant regulations. Investigators and site staff must adhere to these principles.

Standard medical care (prophylactic, diagnostic, and therapeutic procedures) remains the responsibility of the subject's treating physician.

The investigator will inform the sponsor immediately of any urgent safety measures taken to protect the trial subjects against any immediate hazard, as well as of any serious breaches of the protocol or of ICH GCP.

The Boehringer Ingelheim transparency and publication policy can be found on the following web page: trials.boehringer-ingelheim.com. The rights of the investigator and of the sponsor with regard to publication of the results of this trial are described in the investigator contract. As a general rule, no trial results should be published prior to archiving of the CTR.

The terms and conditions of the insurance coverage will be described in the ICF and also stored in the ISF.

8.1 TRIAL APPROVAL, SUBJECT INFORMATION, INFORMED CONSENT

This trial will be initiated only after all required legal documentation has been reviewed and approved by the respective Institutional Review Board (IRB / Independent Ethics Committee (IEC and competent authority (CA) according to national and international regulations. The same applies for the implementation of changes introduced by amendments.

Prior to a subject's participation in the trial, written informed consent must be obtained from each subject (or the subject's legally accepted representative) according to ICH-GCP and to the regulatory and legal requirements of the participating country. Each signature must be personally dated by each signatory and the informed consent and any additional subject-information form retained by the investigator as part of the trial records. A signed copy of the informed consent and any additional subject information must be given to each subject or the subject's legally accepted representative.

The subject must be given sufficient time to consider participation in the trial. The investigator or delegate obtains written consent of the subject's own free will with the informed consent form after confirming that the subject understands the contents. The investigator or delegate must sign (or place a seal on) and date the informed consent form. If a trial collaborator has given a supplementary explanation, the trial collaborator also signs (or places a seal on) and dates the informed consent.

Re-consenting may become necessary when new relevant information becomes available and should be conducted according to the sponsor's instructions.

Proprietary confidential information © 2018 Boehringer Ingelheim International GmbH or one or more of its affiliated companies

The consent and re-consenting process should be properly documented in the source documentation.

